6.2 Stage II – Extended Follow Up

6.2.1 Telephonic Follow Up on Day 42 (+2 days) and Day 60 (+2 days)

During the extended follow up period, the patients will be followed up for AEs or for ‘clinical relapse’ of COVID 19. An additional visit to the hospital (for further assessment) may be scheduled for such patients, if required. Details of concomitant medication will be recorded. The assessments to be performed at an unscheduled visit are mentioned in [Section 6.3.2.3](#) and [Table 2](#).

During the telephonic follow up, the patients will be followed-up for the following reasons:

- a) safety reasons (eg. follow-up on AEs),
- b) to report a clinical relapse of COVID-19 (the patient will be asked if they have had any of the symptoms of COVID-19 after they were discharged).

6.3 Measurements and Evaluations

6.3.1 Stage I – Main Study

6.3.1.1 Visit 1: Screening Visit (Day -3 to Day -1)

- Written informed consent.
- Demographic data (age, gender, nationality, race, height and weight)
- Medical history
- Collection of respiratory tract sample (nasopharyngeal swab or oropharyngeal swab or nasal aspirate or tracheobronchial aspirate) for detection (qualitative) of SARS-CoV-2 (by RT-PCR assay)*
- Serum Pregnancy Test (only for female patients of childbearing potential)*
- Complete physical examination

Study code: NV-05-983-2020
 Protocol No.: CVD-04-CD-001
 Sponsor name: [name], Limited
 Clinical Study Protocol

- Vital signs (SpO₂, body temperature, systolic BP, diastolic BP, pulse rate, and respiratory rate)
- Clinical Status by WHO 10-point ordinal scale
- Clinical Status by 8-point ordinal scale
- NEWS-2 score
- Severity of COVID-19 associated symptoms
- Prior medications
- Chest X-ray*
- 12-Lead ECG*
- Clinical Laboratory assessments (haematology, serum biochemistry and urinalysis)*
- Pre-treatment AEs
- Apply Inclusion and Exclusion Criteria

**Note: Screening investigations, including clinical laboratory evaluations (hematology, serum biochemistry, urinalysis, serum pregnancy test), chest X ray, ECG and RT-PCR assay for detection of SARS-CoV-2 RNA, performed within 72 hours prior to Randomization Day (Day 1) can be considered for eligibility assessments. Refer to [Section 6.3.1.1](#) for further details.*

6.3.1.2 Visit 2: Randomization/Baseline Visit (Day 1)

- Clinical Status by 10-point ordinal scale
- Clinical Status by 8-point ordinal scale
- NEWS-2 score
- Blood oxygen saturation (SpO₂) measurement at rest on room air (i.e., without O₂ supplementation) or alternatively SpO₂/ FiO₂ will be estimated if the patient is on supplemental oxygen, for confirmation of patient eligibility
- Presence/ Absence, and if present, then COVID-19 associated symptom severity assessment
- ICU admission status, supplemental oxygen and mechanical ventilation details
- Partial physical examination
- Vital signs
- Chest X-ray*
- 12 Lead ECG*

Study code: NV-05-983-2020
 Protocol No.: CVD-04-CD-001
 Sponsor name: [name], Limited
 Clinical Study Protocol

- Pre-treatment AEs
- Randomization of patients
- Dosing and compliance assessment
- Treatment emergent AEs
- Concomitant medication

**Note: The investigations (chest X ray and 12 lead ECG) mentioned in Visit 2 - Randomization/Baseline Visit can be waived off if Randomization/Baseline Visit (Visit 2) is being performed on the same day of screening or if the investigations were performed within 72 hours before Randomization/Baseline Visit.*

6.3.1.3 Study period: (Day 2 to Day 27 or discharge, whichever is earlier)

- Clinical Status by 10-point ordinal scale (assessment to be performed once daily on each study day until Day 27 or discharge)
- Clinical Status by 8-point ordinal scale (assessment to be performed once daily on each study day until Day 27 or discharge)
- NEWS-2 score (assessment to be performed once daily on each study day until Day 27 or discharge)
- COVID-19 associated symptom severity assessment (assessment to be performed once daily on each study day until Day 27 or discharge)
- ICU admission status, supplemental oxygen (standard and/or high flow) and mechanical ventilation details (to be collected once daily on each study day until Day 27 or discharge)
- Partial physical examination
- Vital signs
- Treatment emergent AEs
- Concomitant medication
- Dosing (two times in a day) of IMP and assessment of treatment compliance, on each study day until Day 10 or discharge. (Note: *If the patient is discharged before Day 10, the patient will be required to continue the remainder of the IMP treatment course at home. The compliance will be evaluated based on the details in the patient diary*)
- Collection of a respiratory tract sample (nasopharyngeal swab or oropharyngeal swab or nasal aspirate or tracheobronchial aspirate or bronchial lavage) for detection (qualitative) of SARS-CoV-2 (by RT-PCR assay) on Day 5 and Day 10 or discharge

Study code: NV-05-983-2020
 Protocol No.: CVD-04-CD-001
 Sponsor name: [name], Limited
 Clinical Study Protocol

(if discharge happens earlier than one or more of the above-mentioned assessment timepoints)

- Clinical Laboratory assessments (haematology, serum biochemistry and urinalysis) on Day 4, Day 7, Day 10, Day 14 and Day 21 or discharge (if discharge happens earlier than one or more of the above-mentioned assessment timepoints)
- 12 Lead ECG on Day 4, Day 7, Day 10, Day 14 and Day 21 or discharge (if discharge happens earlier than one or more of the above-mentioned assessment timepoints)
- Chest X-ray on Day 4, Day 7, Day 10 and Day 14 or discharge (if discharge happens earlier than one or more of the above-mentioned assessment timepoints)

6.3.1.4 End of treatment assessment [Day 10 (+2 days)]

1. If the patient remains in the hospital until Day 10, the EOT will be performed at the site and all the scheduled assessments for Day 10 mentioned in [Section 6.3.1.3](#) will be performed.
2. If the patient is discharged before Day 10, the EOT can be performed either as an onsite visit or will be performed at the patient's home.

a. On-site visit:

If the patient is able to visit the hospital on Day 10, procedures for an unscheduled visit will be performed.

- COVID-19 associated symptom severity assessment
- Collection of a respiratory tract sample (nasopharyngeal swab or oropharyngeal swab or nasal aspirate or tracheobronchial aspirate or bronchial lavage) for detection (qualitative) of SARS-CoV-2 (by RT-PCR assay)*
- Partial physical examination*
- Vital signs*
- Chest X-ray*
- 12 Lead ECG*
- Clinical Laboratory assessments (haematology, serum biochemistry and urinalysis)*
- Treatment emergent AEs
- Concomitant medication*
- ICU admission status, supplemental oxygen (standard and/or high flow) and mechanical ventilation details*
- Return of empty blister packs and /or unused IMP

Study code: NV-05-983-2020
 Protocol No.: CVD-04-CD-001
 Sponsor name: [name], Limited
 Clinical Study Protocol

** Assessments may be performed at Investigator's discretion for individual patients for evaluation of patient safety or follow up of adverse events.*

OR

b. At home:

If the patient is unable to visit the hospital for the EOT, the below procedures will be performed.

- Study nurse or phlebotomist will visit the patient at his/her residence
- Blood sample collection for clinical laboratory assessments (haematology, serum biochemistry)
- A nasopharyngeal swab or oropharyngeal swab will be collected from the patient and sent for detection (qualitative) of SARS-CoV-2 RNA by RT-PCR assay based on Investigator's discretion for individual patients
- Collection of empty blister packs and /or unused IMP
- A telephonic follow up will be performed to assess the below
 - Treatment emergent AEs
 - COVID-19 associated symptom enquiry for assessment of clinical relapse
 - Concomitant medication

6.3.1.5 Visit 3: End of Study-Day 28 (+2 days) or discharge or study discontinuation whichever is earlier

- Serum Pregnancy Test (only for female patients of childbearing potential)
- Clinical Status by 10-point ordinal scale
- Clinical Status by 8-point ordinal scale
- NEWS-2 score
- COVID-19 associated symptom severity assessment
- ICU admission status, supplemental oxygen (standard and/or high flow) and mechanical ventilation details
- Collection of a respiratory tract sample (nasopharyngeal swab or oropharyngeal swab or nasal aspirate or tracheobronchial aspirate or bronchial lavage) for detection (qualitative) of SARS-CoV-2 (by RT-PCR assay)
- Partial physical examination
- Vital signs
- Chest X-ray

Study code: NV-05-983-2020
 Protocol No.: CVD-04-CD-001
 Sponsor name: [name], Limited
 Clinical Study Protocol

- 12 Lead ECG
- Clinical Laboratory assessments (haematology, serum biochemistry and urinalysis)
- Treatment emergent AEs
- Concomitant medication

6.3.1.6 Telephonic follow up on Day 10, Day 14, Day 21 and Day 28, as applicable for the individual patient

For patients who are discharged before Day 28, a telephonic follow up assessment will be performed on Days 10 (applicable only for patients who are discharged earlier than Day 10 and if patients are unable to visit the site for EOT on Day 10), 14, 21 and 28 *as applicable for the individual patient* (window period for telephonic follow up is +2 days from scheduled day of follow up).

- Treatment emergent AEs
- COVID-19 associated symptom enquiry for assessment of clinical relapse
- Concomitant medication

6.3.1.7 Unscheduled Visit: If further assessment is found to be necessary on Telephonic Follow up

- COVID-19 associated symptom severity assessment
- Collection of a respiratory tract sample (nasopharyngeal swab or oropharyngeal swab or nasal aspirate or tracheobronchial aspirate or bronchial lavage) for detection (qualitative) of SARS-CoV-2 (by RT-PCR assay)*
- Partial physical examination*
- Vital signs*
- Chest X-ray*
- 12 Lead ECG*
- Clinical Laboratory assessments (haematology, serum biochemistry and urinalysis)*
- Treatment emergent AEs
- Concomitant medication*
- ICU admission status, supplemental oxygen (standard and/or high flow) and mechanical ventilation details*

** Assessments maybe performed at Investigator's discretion for individual patients for evaluation of patient safety or follow up of adverse events.*

Study code: NV-05-983-2020
Protocol No.: CVD-04-CD-001
Sponsor name: [name], Limited
Clinical Study Protocol

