1.1.4 Clinical Experience

JP 120 study was a 22-Day repeated dose study on favipiravir investigation of the pharmacokinetics, safety and tolerability in healthy subjects. In the JP120 study, favipiravir was administered at 1,800/800 mg BID, which is the same dosage as in this clinical study, in repeated doses for 22 days, the maximum observed plasma concentration (C_{max}) was approximately 65 $\mu\text{g}/\text{mL}$ after the first dose on Day 1 and approximately 100 $\mu\text{g}/\text{mL}$ after the first dose on Day 12 and after administration on Day 22. The area under the plasma concentration-time curve (AUC) was approximately 720 $\mu\text{g}\cdot\text{hr}/\text{mL}$ after the first dose on Day 1, the AUC during repeated dose intervals (AUC_{τ}) after the first dose on Day 12 and after administration on Day 22 was approximately 950 $\mu\text{g}\cdot\text{hr}/\text{mL}$. The C_{min} remained at approximately 56 to 75 $\mu\text{g}/\text{mL}$ after the second dose on Day 1 and onward.

Also, in the JP120 study, there were no serious adverse events (SAEs) including death or any significant AEs. The incidence of AEs was 100% (8/8 subjects, 16 events) in the favipiravir group and 1/2 subjects (1 event) in the placebo group. The incidence of AEs that occurred was as follows. In the favipiravir group: blood uric acid increase was 100% (8/8 subjects, 8 events), alanine aminotransferase (ALT) increased, aspartate aminotransferase (AST) increased, and white blood cells urine positive were each 25.0% (2/8 subjects, 2 events), and abdominal pain upper and rash were each 12.5% (1/8 subjects, 1 events). In the placebo group: the incidence of protein urine present was 1/2 subjects (1 event). The AEs that occurred in the JP120 study were all AEs for which a causal relationship with the investigational drug cannot be ruled out, except for white blood cells urine positive, which occurred in the favipiravir group. All AEs that occurred were mild in severity and resolved without any treatment. Based on the above, the safety and tolerability of favipiravir administered for 22 days were confirmed.

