If patient is discharged from the hospital before Day 28, the assessments mentioned in the end of study visit (Day 28) will be performed before the patient is discharged. After discharge, telephonic

Study code: NV-05-983-2020
Protocol No.: CVD-04-CD-001
Sponsor name: [name], Limited
Clinical Study Protocol

follow up will be performed on Day 10 (applicable only for patients who are discharged earlier than Day 10 and if patients are unable to visit the site for EOT on Day 10), Day 14, Day 21 and Day 28. The telephonic follow up will be as applicable for the individual patient, depending upon the actual day when (s)he is discharged. A 2-day window period is allowed for telephonic follow up.

In case the patient remains admitted in the hospital beyond Study Day 28, the end of study assessments will be performed for the patient on Day 28 (+2) days.

Stage I of the study will be completed when the 'Day 28' assessment is completed either as an in-patient assessment if the patient is still hospitalized, or as a telephonic follow up assessment if the patients are discharged earlier to Day 28.

Once all the patients complete the Stage I of the study, the database would be locked, and analysis will be performed.

Stage II – Extended Follow Up:

All the patients will be followed up for AEs or for 'clinical relapse' of COVID 19. Two telephonic follow up assessments will be performed on Day 42 and Day 60. An additional visit to the hospital (for further assessment) may be scheduled for such patients, if required. A 2-day window period is allowed for telephonic follow up.

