3.1.6.2 Study Treatment Discontinuation

3.1.6.2.1 Study treatment discontinuation criteria

When a patient meets any of the following criteria, the Principal Investigator or a Sub-Investigator will discontinue administering the study drug to that patient.

- a. The patient requests withdrawal from the clinical study
- b. If the patient requests discontinuation of administration of the study drug
- c. The patient died
- d. The patient is lost to follow-up
- e. If an AE occurs and the Principal Investigator or a medically qualified Sub-Investigator judges that continuing with the administration of the study drug would not be in the interest of patient's safety or well-being
- f. If a patient experiences a serious adverse event assessed by Investigator and/or Medical Monitor to be reasonably causally related to the IMP (FPV/Placebo)
- g. If a patient becomes pregnant while receiving IMP (FPV/Placebo)
- h. If patient's serum uric acid or hepatic transaminases levels are assessed as Grade 3 severity by National Institutes of Health (NIH) National Cancer Institute (NCI) Common Terminology Criteria for Adverse Events (CTCAE)²³, at any timepoint during the treatment period
- i. If a patient is otherwise deemed ineligible to continue in the study by the Principal Investigator or a Sub-Investigator
- j. Upon request by the CRO or Sponsor Medical Monitor (with appropriate justification)

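### For patients discharged before Day 10, end-of-treatment blood tests are required on the home route but discretionary on the on-site route, so Day 10 laboratory data may be selectively missing

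*Protocol*

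**What the plan says.** Protocol 6.3.1.4 gives a patient discharged before Day 10 two ways to complete the EOT assessment, with a window of Day 10 to Day 12 (6.1.3).

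- **On site (2a).** Unscheduled-visit procedures apply. The list includes "Clinical Laboratory assessments (haematology, serum biochemistry and urinalysis"), marked with an asterisk that is explained as "Assessments may be performed at Investigator's discretion for individual patients for evaluation of patient safety or follow up of adverse events".
- **At home (2b).** A nurse or phlebotomist visits, and "Blood sample collection for clinical laboratory assessments (haematology, serum biochemistry") is listed with no discretion. Only the swab is left to the investigator.

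While the patient is in hospital, 6.3.1.3 schedules "Clinical Laboratory assessments (haematology, serum biochemistry and urinalysis) on Day 4, Day 7, Day 10, Day 14 and Day 21 or discharge" if that comes earlier. Section 3.1.1 adds that on early discharge "the assessments mentioned in the end of study visit (Day 28) will be performed before the patient is discharged", and the list in 6.3.1.5 includes laboratory tests. Scheduled contact after EOT is by telephone.

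Table 2 marks laboratory evaluations at Day 10. Section 7.2.1 and SAP 10.7.2 list Day 10 among the laboratory timepoints.

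Stopping criterion (h) in 3.1.6.2.1 reads "If patient's serum uric acid or hepatic transaminases levels are assessed as Grade 3 severity" and applies "at any timepoint during the treatment period".

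**The concern.** The protocol sends staff to a patient's residence to draw safety blood, yet does not require the same sample from a patient who has come to the hospital for the same assessment. The discretionary wording suits a visit prompted by a problem. Here it governs a planned visit.

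Section 1.3 names raised uric acid, AST and ALT as risks. Section 1.1.4 reports that, in healthy subjects at this dosage, "blood uric acid increase was 100% (8/8 subjects, 8 events"), with ALT and AST raised in 2 of 8 each. These rises can be silent. Under section 9.1 an abnormal laboratory value becomes an adverse event only after it has been measured and judged clinically significant, so a telephone call will not find one.

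At stake are the end-of-treatment safety data. Day 10 summaries would pool inpatients, home-visit patients and those on-site patients whom an investigator chose to test. Who is missing would depend on early discharge, which is close to the efficacy outcome, and on suspicion of toxicity.

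**Working it through.** The plan states no figure on this point, so there is nothing to reproduce. The check is a comparison of schedules, a count of days and doses, and a range for the number affected.

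**1. The two routes side by side (6.3.1.4)**

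| Item | On site (2a) | At home (2b) |
|---|---|---|
| Haematology, serum biochemistry | discretionary | listed |
| Urinalysis | discretionary | not listed |
| ECG, vital signs, partial examination | discretionary | not listed |
| Adverse event enquiry | listed | listed (telephone) |

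**2. What is measured before and after discharge**

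Inputs: laboratory days 4, 7 and 10 or discharge (6.3.1.3); laboratory tests at every early discharge (3.1.1, 6.3.1.5); two doses a day for 10 days, so 2 × 10 = 20 doses; no dosing after Day 10 (3.1.2); EOT on Day 10 to 12 (6.1.3). Assume both doses on the day of discharge are taken before going home. For discharge on Day d, home days = 10 − d, home doses = 2 × (10 − d), and the home-route draw comes 10 − d to 12 − d days after discharge.

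| Discharge day | Required post-baseline tests by discharge | Home days | Home doses | Days to home-route draw |
|---|---|---|---|---|
| 2 | 1 | 8 | 16 | 8–10 |
| 3 | 1 | 7 | 14 | 7–9 |
| 4 | 1 | 6 | 12 | 6–8 |
| 5 | 2 | 5 | 10 | 5–7 |
| 6 | 2 | 4 | 8 | 4–6 |
| 7 | 2 | 3 | 6 | 3–5 |
| 8 | 3 | 2 | 4 | 2–4 |
| 9 | 3 | 1 | 2 | 1–3 |

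Three things follow.

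- Every early-discharged patient has at least one required post-baseline test.
- On the on-site route no required test follows discharge. A patient who leaves on Day 4 and is not tested at EOT has no laboratory value covering the last 12 of 20 doses.
- Neither route has a test between discharge and EOT. At a Day 10 draw at most 2 of 20 doses remain; on Day 11 or 12 none do.

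An early discharge sample is not a clear substitute for an end-of-treatment one. Section 1.1.4 gives a peak concentration of about 65 µg/mL after the first dose, and section 1.2 gives about 87 to 104 µg/mL from Day 5 onward.

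**3. How many patients**

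The documents give neither the proportion discharged before Day 10 nor the share attending on site. Both are assumptions here. Number with no required EOT value = 780 × f × s.

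| Discharged before Day 10 (f) | s = 25% on site | s = 50% | s = 75% |
|---|---|---|---|
| 20% | 39 | 78 | 117 |
| 40% | 78 | 156 | 234 |
| 60% | 117 | 234 | 351 |

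These counts cover both arms. They are patients for whom the test is optional; how many would go untested depends on the investigators.

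**The case against.** **This is a consistent design choice.** The on-site EOT is defined by unscheduled-visit procedures in the synopsis, in 3.1.1, 3.1.5 and 6.1.3, and in SAP 8.1.1. Footnote 5 to Table 2 sends early-discharged patients to 6.3.1.4, so the Day 10 mark is qualified, and SAP 10.7.2 carries wording about earlier discharge. This stands to the extent that the schedule is not a flat contradiction. It does not explain why blood is required by one route and optional by the other. Section 7.2.1 and SAP 10.7.2 also say nothing about how optional Day 10 values are to be read.

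**The footnote allows tests for patient safety.** True, and adverse event enquiry is not discretionary on site. So the most that can be said is that values may be missing. Discretion also makes testing more likely where toxicity is suspected, which is a selection problem in itself.

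**The home route omits more than it adds.** It has no urinalysis, ECG, vital signs or examination. This stands, and limits the remedy to the blood sample the home route already takes.

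**The background signals are modest.** The events in the 8 healthy subjects were all mild and resolved without treatment. The 7/30 hyperuricaemia and 6/30 raised uric acid come from another disease (SFTS). In the open-label COVID-19 study, uric acid rose in 16 of 116 patients at a lower dosage. Fair, but these are still the laboratory effects the protocol singles out for stopping treatment.

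**Two stronger readings are tempting and are not supported.** A reader might infer that criterion (h) has no data to act on. It has the Day 4, Day 7 and discharge results, as applicable. Its gap runs from discharge to EOT, is the same on both routes, and would hardly be narrowed by an EOT draw. A reader might also infer bias in whichever arm recovers faster. The documents give no difference between arms in early discharge, the trial is double-blind, and testing on suspicion could raise or lower an observed Grade 3 rate.

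**Conclusion.** The point holds for the end-of-treatment safety data. For patients discharged before Day 10, haematology and serum biochemistry at EOT are required at home and optional on site, with no later scheduled test. End-of-treatment uric acid, ALT and AST may be missing for on-site patients, and Day 10 summaries may be selectively incomplete. The size is 39 to 351 of 780 patients without a required value, resting wholly on the assumed ranges of 20–60% discharged before Day 10 and 25–75% of those attending on site. The direction of any distortion, and any difference between arms, cannot be derived from the documents. The primary efficacy analysis is not touched.

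A separate inconsistency remains. Criterion (h) is said to apply throughout the treatment period, but neither route schedules a laboratory test during home dosing. The optional on-site test does not cause this.

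**What to change.** 1. **Protocol.** Reconcile 6.3.1.4(2a) with 6.3.1.4(2b), Table 2, section 7.2.1 and SAP 10.7.2 so that the same blood sample, haematology and serum biochemistry only, is collected at EOT by either route. Simply deleting the asterisk would also make urinalysis compulsory on site and so create a new difference from the home route.
2. **Consistency.** Carry the change through every place that defines the on-site EOT by unscheduled-visit procedures: the synopsis (Study Duration), 3.1.1, 3.1.5, 6.1.3 and SAP 8.1.1. Keep the discretionary wording for true unscheduled visits (6.3.1.7, 6.3.2.3).
3. **SAP 10.7.2.** Add, by arm, each patient's worst value from first dose through EOT for uric acid, ALT and AST, so that patients contribute whatever day they left hospital. Report beside it how many had an EOT sample, because a worst value cannot recover what was never drawn.
4. **Criterion (h).** The sponsor should reconcile 3.1.6.2.1(h) with the absence of scheduled tests during home dosing and state how the criterion applies between discharge and EOT. No clinical rule is proposed here.

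The cost is a small local laboratory charge at a visit that already takes place, one SAP table, and a protocol amendment touching several sections, with the ethics committee handling that section 12.8 requires.
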